1. INTRODUCTION

1.1 Background

On the 14th June 2017 a fire broke out on the fourth floor of the 24-storey Grenfell Tower in west London, causing the deaths of over 70 occupants and becoming the worst residential fire in the United Kingdom since the second world war. The fire spread unusually rapidly and its extinction – which took 60 hours - required the labour of over 1000 firefighters from the London Fire Brigade (LFB). No firefighters died at the scene and none required emergency medical care for smoke inhalation. Because of the scale and nature of the fire, however, a sizeable proportion of them were subjected to unusually high exposures to fire smoke, in many cases without standard respiratory protection; we propose to establish a cohort of the Grenfell firefighters to study a range of potential adverse effects from these exposures.

Cardiorespiratory disease

The acute, non-burn, effects of exposure to fire smoke are reasonably well understood and are largely respiratory (1), but they include also systemic effects, such as those induced by exposure to products of pyrolysis such as hydrogen cyanide, benzene or acroleins, and – probably - cardiovascular effects (2). The evidence around longer-term, adverse outcomes of firefighting – and indeed smoke inhalation in general - is scanty, more complex and likely to be confounded by international and temporal differences in recruitment, retention, routine health surveillance and practice, including the use of personal protective equipment. These make generalisations very difficult.

A systematic review of the cumulative effects of firefighting on lung function has recently been published (3). It includes 22 studies whose findings are 'highly variable and provide an unclear picture of how the rate of change in lung function of firefighters relates to routine exposures; moreover the evidence for an 'exposure-response' relationship is not compelling'. The reasons for the discrepancies between studies probably embrace those listed above but will include also differences, and insensitivities, in the functional measures used and in the estimations of exposure to fire smoke which, with very few exceptions (4), are both crude and by self-report, and so likely to be open to misclassification and the obscuring of exposure-response relationships. Small airway damage is a plausible response to fire smoke inhalation (5), but most studies have relied on relatively crude spirometric measurements which may not detect obstructive changes in the smaller airways; in a survey of around 500 Australian firefighters, for example, the use of impulse oscillometry identified airways dysfunction even when spirometry values were normal (6) – although no relationship with exposure to fire smoke was evident. In the absence of sufficient longitudinal data, the prognostic significance of asymptomatic small airways disease is unclear but it is generally accepted that it presages more significant airflow obstruction in smokers (7); a recent editorial suggests that "differences in the small airways (even those that do not appreciably affect FEV_1) might also predict the development of asthma or COPD" (8). Moreover, acute exposure to inhaled irritants may give rise, in the conducting airways, to a complex interaction of inflammation, smooth muscle activation and neuronal inputs that create and perpetuate both fixed and reversible airflow obstruction. Bronchial hyperreactivity itself is another plausible outcome (9), but again has seldom been studied. An exception is a survey of 400 Dutch firefighters, most of them volunteers, in whom the dose-response slope to metacholine challenge was significantly and independently associated with the number of fires fought in the last year; limiting the analysis to firefighters without exposure within seven days of testing did not change the association (10). There have been just two studies of

lung function in UK firefighters (11, 12). Both were longitudinal, although one over just 12 months, and

both were undertaken over 30 years ago; neither showed any adverse effects attributable to firefighting.

Studies such as these are designed to reflect cumulative exposure(s) to repeated, relatively lowintensity events and their findings may not be applicable to those who fought the Grenfell fire. In a manner similar to that of the Grenfell firefighters, rescue and other workers at the World Trade Center (WTC) in 2001 experienced an abrupt and substantial, increase in exposure. While comparisons must be limited by the very different natures of the exposures (respectively, fire smoke vs dust of high alkalinity), increased rates of respiratory symptoms, airflow obstruction and bronchial hyperreactivity, and a stepwise fall in lung function, have been reported in WTC workers (13, 14). There has been only one other study of firefighters exposed to non-routine firefighting. Twenty (of 175) firefighters who extinguished an unusually intense chemical fire in Houston were followed over 18 months, during which they experienced, on average, declines in FEV1 and FVC of 122ml and 62ml respectively (15); the study is limited not only by its size but also by the lack of any pre-event spirometry.

The established relationships between exposure to fine particulate matter and cardiovascular diseases have led some to question whether the risks of the latter are increased in firefighters. Sudden cardiac death accounts for the largest share (c.40%) of on-duty cardiac deaths among firefighters – surpassing burns, trauma, asphyxiation and smoke inhalation. They most commonly coincide with active strenuous duties (16) suggesting that the physical and environmental hazards faced by firefighters acutely magnify their cardiovascular risk in the peri-emergency setting. Studies of US firefighters have reported increases in several adverse measures of arterial stiffness following three hours of firefighting activity (17) and decreased microvascular function and alterations in heart rate variability after fire training (18). A cross-sectional survey of US wildfire fighters reported a (tenuous) link between exposure and increased arterial stiffness (2). More broadly, a systematic review of prognostic studies concluded that central haemodynamic indices are independent predictors of future cardiovascular events and all-cause mortality; for example, a 10% increase in augmentation index was associated with a 26% increase in the risk of future coronary disease (19). Despite this, a recent analysis of a cohort of around 10,000 Danish firefighters (20) reported only a modest increase in the standardised incidence ratio of all cardiovascular diseases (SIR 1.10, 95%ci 1.05-1.15); the estimates and their precision, however, depended on whether reference was made to a general or military population.

Malignancy

Finally, there is concern that work as a firefighter increases the risk of malignant disease; the relevant literature is broad, and again somewhat inconsistent. The spectrum of toxic substances and metabolites produced by structural fires is wide and often unpredictable, but common components of fire smoke include several established human carcinogens such as benzene, polycyclic aromatic hydrocarbons, polychlorinated biphenyls, asbestos, arsenic, 1,3-butadiene, formaldehyde and cadmium (21). Exposures to fire smoke are, of course, intermittent and in many cases infrequent (see (21) but the routes of exposure for firefighters are not only respiratory but also dermal, including through the use of contaminated clothing and protective equipment (22), and perhaps more prolonged. The epidemiological evidence for cancer risks is, as above, likely to be confounded,

London

and further so by both lifestyle factors and by ascertainment bias. Two systematic reviews are available (21, 23) and suggest modest increases in risk for some non-solid organ cancers and for cancers of the testis and prostate and for melanoma. A more recent analysis of a cohort of around 10,000 Danish firefighters (20), however, reported no significant increase in the standardised incidence ratios of all

cancers (SIR 1.02, 95%ci 0.96-1.09). There have been no epidemiological studies of cancer in UK firefighters.

There have been several short-term molecular studies of cancer risk in firefighters; IARC (21) lists six, with varying results and none of more than about 50 subjects. A typical, more recent, example is of 53 Danish recruits undergoing fire-training (24); on the basis of an association between the level of DNA strand breaks with dermal exposure to pyrene and total PAHs, the authors conclude that firefighting activity is associated with cell genotoxicity. It is well accepted, too, that environmental exposures are associated with epigenetic change, ranging from alterations in DNA and RNA methylation patterns to changes in the expression of small non-coding RNAs. Although there are no studies examining changes to the epigenomes of firefighters following occupational smoke inhalation or through dermal routes, there are data to show that exposure leaves long term DNA methylation changes that can be detected in blood samples. For example, DNA methylation leaves a long-term signature of cigarette smoking that can be detected in blood samples more than 20-years after smoking has ceased (25, 26) and, similarly, occupational exposure to ionising radiation was found to leave a defined signature 2-4 years after a single exposure event (27). Therefore it should be possible to examine changes in, for example, the epigenome in blood of firefighters to obtain an exposure-related signature.

As above, much of the research into the long-term effects of smoke inhalation has been undertaken in firefighters; studies of surviving fire victims are very few and very limited in scope. Two years after the event, small airways damage was detected in 14 passengers caught in the King's Cross fire in London (5), selected from those with reported 'smoke inhalation' during the incident suggesting that damage may accrue in those most intensely exposed. Airway hyper-reactivity and bronchial inflammation were identified in a small sample of survivors of the Inchon bar fire in South Korea, 1999 (28). There appears to be no published evidence relating to cardiovascular or cancer outcomes in non-professional populations.

Hence, with the exception of the WTC event, the available evidence on respiratory damage following an unusually intense firefighting operation is limited to a single, small study undertaken almost 40 years ago. While its findings suggest an accelerated rate of lung function decline, its relevance to those involved in the Grenfell Tower fire is doubtful. Similarly, there is no large-scale evidence relating to medium-term cardiovascular outcomes or to epi(genetic) DNA damage after intense firesmoke exposure.

1.2 Study Rationale

The Grenfell firefighter population offers a rare opportunity to study the effects of intense fire smoke inhalation on a range of mid- and long-term outcomes. The population is readily defined and enumerated and can, through contemporary records, be subdivided into descending categories of exposure at the Grenfell fire, allowing internal comparisons in the assessment of cause and effect.

London

Importantly, and uniquely, detailed records held by the LFB will provide an objective, semiquantitative estimate of professional exposure to fire smoke before and after the Grenfell incident; moreover, periodic, three-yearly health surveillance, undertaken as a condition of active employment at LFB, will provide pre-incident information on lung health including spirometry.

2. STUDY OBJECTIVES

We aim to establish a **Grenfell Firefighters cohort** with the purpose of identifying and measuring any adverse cardio-respiratory outcomes incurred through occupational exposure to fire smoke at the Grenfell fire. In addition and by accounting for prior and subsequent exposures to fire smoke, the cohort will provide unique information on the frequency and nature of the mid- and long-term adverse effects of active firefighting and smoke-inhalation in general.

This protocol is to establish the cohort. To do this we aim to:

- 1. identify the exposed population, together with a smaller, referent sample of eligible but unexposed firefighters
- 2. invite each member of the cohort to enrol in a long-term, prospective study and to obtain individual permissions for long-term linkage to routinely collected health data
- 3. obtain semi-quantitative measures of exposure to firesmoke at Grenfell and at other fires
- 4. undertake a baseline survey of respiratory and cardiac physiology and to link these to Grenfell firesmoke exposure estimates, to inform our mechanistic understanding of any subsequently identified long-term outcomes
- collect biosamples for future use in 'omic analyses of outcomes (such as malignancy), probably within nested case-control studies.
 Dependent on our findings in the baseline survey, subsequent follow-up of the cohort may require further face-to-face study but may be more efficiently undertaken by data linkage alone.

3. STUDY DESIGN AND METHODS

3.1 Design and procedures

On our behalf, to satisfy the requirements of GDRP, LFB will identify the names and contact details of all firefighters who directly attended the Grenfell Tower fire in June 2017; every effort will be made to include those who have left service since the fire, estimated to number no more than a dozen. In addition we will ask LFB to identify a random sample (n=100) of firefighters from stations close to Grenfell Tower who would have been eligible to attend the fire but did not do so because of annual leave.

Each of the above will be invited, by the Brigade, to contact us with regard to enrolling in a long-term, prospective study.

Those who do so make contact will be invited to:

London

- 1. provide consent to, and the necessary information (name, date of birth, sex, NHS number and contact details) for prospective linkage to national registers including those of mortality, cancer incidence, hospital admission and A/E attendance, and GP consultations.
- provide consent for their individual histories of employment and firesmoke exposure at and other than Grenfell to be released to Imperial College by LFB, and for this information to be periodically updated; and to provider similar consent for access to their past and subsequent lung function measurements made in the normal course of their employment by LFB.
- 3. participate in an independent and confidential survey of (cardio)respiratory health, to take place in the clinical research facility of Royal Brompton hospital in London. For those who choose to take part, we will collect the consents and information in 1 and 2 above at the time of survey; for the remainder we will communicate by post, and include the questionnaire outlined below.

For the baseline survey, we have elected to use investigative methods which are well-established and which can be completed fairly rapidly; moreover, our tests need to be minimally invasive since it will be essential that participation in the project will not impede an immediate return to active work.

The information we propose to collect is listed below:

A. Demographics and confounding exposures

Through self-completed questionnaire, the collection of some simple demographic and lifestyle information, to include:

- age/sex
- duration of employment as a firefighter
- smoking: detailed (pack years; age of starting/quitting)
- other, relevant occupational and non-occupational exposures
- other relevant ill-health and medications

Participants will be invited to complete the questionnaire using a web-based tool designed specifically for this study.

B. Respiratory health assessment

• a respiratory symptoms questionnaire incorporating standardised questions that focus on breathlessness and cough, modified from the Dyspnoea 12 instrument; to include also an enquiry into prior respiratory health, diagnoses and relevant treatments

• small airways function; we will measure resistance of the respiratory tract at 5 and 20 Hz (R5 and R20) using impulse oscillometry (Master Screen Spirometry-IOS System, Jaeger, Germany). Participants will be seated and will undertake a minimum of three trials, each lasting 30s, during tidal breathing while firmly supporting their cheeks with their hands.

• spirometry: following oscillometry and using a standard, electronic spirometer (Vitalograph, Buckingham, UK) in accordance with internationally accepted guidelines (29), we will measure FEV₁, FVC and small airway flows.

• bronchodilator reversibility: the above measurements of lung function will be repeated 15 minutes after the administration of a bronchodilator (400µg inhaled salbutamol through a 'spacer' device).

C. Cardiovascular health assessment

• arterial stiffness: we will measure pulse wave velocity and augmentation index using a Vicorder (Skidmore Medical, Bristol, UK). Central aortic pulse wave velocity will be defined as the

London

ratio of pulse wave transit time and distance between the carotid and femoral arteries and augmentation index by the enhancement of central aortic pressure by a reflected pulse wave.

D. Biosampling: we do not plan to undertake analyses of these samples within this project but will retain them for future work to examine – at a later date - epigenetic and other 'omic changes

- a venous blood sample (serum and plasma)
- a urine sample

After collection and processing, the samples will be stored in a dedicated freezer at -80°C.

Firesmoke exposure assessment:

Grenfell

• we will, with experts from LFB and with the use of contemporaneous records, develop a tool which will provide semi-quantitative estimates, for all consenting cohort members, of individual exposure to fire smoke during the Grenfell fire.

pre- and post-Grenfell

 we will, for each consenting member of the cohort, use the detailed information, held by LFB, on individual incidents of smoke inhalation documented as a 'safety event/injury' supplemented by station-specific 'operational experience' linked to employment records for each firefighter; see box. This will provide an unprecedented, objective measure of the non-Grenfell fire experience for each participant.

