assumption. There is not yet an established minimal clinically important difference for R5 (or other oscillometry values) but it will almost certainly be >0.02; our intent, however, would be simply to compare values across exposure strata to establish cause/effect.

The primary statistical analysis will be of the relationship between R5 and 'Grenfell exposure', an independent, ordinal variable with several levels including nil. Secondary analyses will be of other, continuous and categorical measures of respiratory function and symptoms and of arterial stiffness. Univariable analyses will be through ANOVA or Kruskall Wallis (as appropriate) with a non-parametric test of trend, an extension of the Wilcoxon rank-sum test. We will subsequently undertake linear regression analyses adjusting for non-Grenfell firesmoke exposures (likely a continuous measure) and other potential confounders including age, sex, ethnicity, BMI, smoking and other non-firefighting occupational exposures (Yes/No).

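### The non-Grenfell smoke covariate does not separate exposure before the fire from exposure after it, although post-fire exposure, partly counted from injury reports, may depend on the airway damage under study

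*Protocol*

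**What the plan says.** Protocol section 1.2 expects LFB records to give a "semiquantitative estimate of professional exposure to fire smoke before and after the Grenfell incident". Section 2 states the aim of "by accounting for prior and subsequent exposures to fire smoke".

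Section 3.1, under the label "pre- and post-Grenfell", describes the source as "individual incidents of smoke inhalation documented as a" safety event or injury, to which it adds the operational experience of each station, tied to individual employment records. It calls the result an "objective measure of the non-Grenfell fire experience for each participant".

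Section 3.2 plans unadjusted comparisons of R5 across Grenfell exposure levels, then linear regression "adjusting for non-Grenfell firesmoke exposures (likely a continuous measure) and other potential confounders". The word *other* places the smoke measure itself among the confounders. The same section lists other smoke exposure as potentially confounding in the later linkage analyses. The text nowhere divides the measure at June 2017 for analysis, and nowhere considers that post-fire exposure might be affected by Grenfell exposure or its consequences.

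**The concern.** The primary hypothesis in section 3.2 is causal: intense exposure at Grenfell produced a small-airways deficit. Pre-fire smoke is an ordinary candidate confounder. Post-fire smoke is different, because it comes after the exposure under study and may lie downstream of it.

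Two routes are plausible. First, a smoke-inhalation injury report records a reaction as well as a dose, so it may be filed more readily by someone with reactive airways. Second, employment records carry any change of duty, and section 1.2 makes health surveillance a condition of active employment. Conditioning on a variable that the damage itself moves can distort the Grenfell coefficient. If both periods sit in one number, a reader of the adjusted result cannot tell that this has happened.

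**Working it through.** **Inputs from Protocol section 3.2.** R5 SD 0.08 kPa/L/s; 100 heavily and 900 less exposed firefighters with 80% taking part, so 80 and 720; difference 0.027; alpha 0.05, sidedness not stated.

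**The plan's own figure.** SE = 0.08 × √(1/80 + 1/720) = 0.0094, and 0.027/0.0094 = 2.86. Power is Φ(2.86 − 1.96) = 81.7% two-sided and Φ(2.86 − 1.645) = 88.9% one-sided. The stated 90% is approached one-sided, or two-sided with all 100 and 900 taking part (89.3%). This does not decide the present point; the figures serve only as a scale.

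**Illustration of pooled adjustment.** The documents give no strength for any path, so the following are assumptions.
- Airway state after the fire: D = 0.027G + e, where G marks heavy exposure and e has SD 0.08.
- Pre-fire exposure P has SD 1 and is r higher in the heavily exposed. r = 0 matches the balance that section 3.2 assumes.
- Recorded post-fire exposure: F = u + aD/0.08, with u of SD 1. So a is the SD change in recorded exposure per SD of damage.
- R5 = D + 0.008P + 0.008F.

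Total Grenfell effect: T = 0.027(1 + 0.1a).

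Slope of R5 on P + F within exposure group: B = [0.016 + 0.08a(1 + 0.1a)]/(2 + a²).

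Grenfell coefficient after pooled adjustment: T + 0.008r − B(0.3375a + r).

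Example, a = +0.4 and r = 0: T = 0.02808; B = (0.016 + 0.03328)/2.16 = 0.0228; coefficient = 0.02808 − 0.0228 × 0.135 = 0.0250, which is 11% below T.

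| a | r | Total effect | Pooled adjustment | Departure |
|---|---|---|---|---|
| 0 | 0 | 0.0270 | 0.0270 | 0% |
| −0.2 | 0 | 0.0265 | 0.0265 | 0% |
| +0.2 | 0 | 0.0275 | 0.0265 | −4% |
| −0.4 | 0 | 0.0259 | 0.0250 | −4% |
| +0.4 | 0 | 0.0281 | 0.0250 | −11% |
| −0.6 | 0 | 0.0254 | 0.0229 | −10% |
| +0.6 | 0 | 0.0286 | 0.0229 | −20% |
| 0 | 0.3 | 0.0270 | 0.0270 | 0% |
| −0.4 | 0.3 | 0.0259 | 0.0294 | +14% |
| +0.4 | 0.3 | 0.0281 | 0.0206 | −27% |

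A simulation of the same model with 1,000,000 subjects agreed to within about 0.0003. Adjusting for P alone recovered T in every row.

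**Splitting is not enough by itself.** With P and F as separate terms, the coefficient is 0.027/(1 + a²), or 0.0233 at a = ±0.4. That is still below T, because the damage-driven record remains in the model.

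**The injury-report path alone.** Suppose a yes/no post-fire report occurs in 10% or 30% of participants, with odds rising 1.5-, 2- or 3-fold per SD of R5 (assumed). By simulation, the ratio of adjusted to unadjusted estimate is:

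| Odds ratio | 10% reporting | 30% reporting |
|---|---|---|
| 1.5 | 0.985 | 0.968 |
| 2 | 0.958 | 0.915 |
| 3 | 0.908 | 0.818 |

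This is shrinkage of about 1 to 18%. The planned measure is broader than one report. If reports supplied 25 to 50% of its variance (assumed), shrinkage would be about 0.4 to 9%.

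**The opposite error.** Suppose post-fire exposure is higher in the heavily exposed only because of station, by 0.2, 0.3 or 0.5 SD (assumed). A pre-fire-only model then leaves in 0.008 times that amount: 0.0286 (+6%), 0.0294 (+9%) or 0.0310 (+15%) in place of 0.027. Adjusting for post-fire exposure would remove this.

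**Scale.** The largest departure in the first table is 0.0281 − 0.0206 = 0.0075, about 0.8 SE. Most others are below 0.4 SE.

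**The case against.** Several counter-arguments have force.

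- **Pooling is inferred.** Section 3.2 speaks of exposures in the plural and of a measure that is only likely to be continuous. Sections 1.2 and 2 name the two periods, and a statistical analysis plan not shown could separate them. It would be too strong to say that the protocol commits to one pooled number. What stands is that the text defines one measure, treats it as a confounder and gives no split.
- **Post-fire exposure can matter as a confounding path.** A reader might infer that only pre-fire exposure can confound. The documents do not support that. Station or role could drive both Grenfell exposure and later exposure, later smoke may itself affect R5, and neither station nor role is a listed covariate. Section 2 also aims to account for later exposure. This stands in full and shapes the fix.
- **Leaving service is a minor route.** Sections 3.1 and 4.1 put leavers at no more than a dozen of about 1,000, or about 1%. The reporting route does not depend on leaving, but neither it nor redeployment is documented. Section 1.1 also describes small-airways disease as possibly asymptomatic, which argues against strong reporting effects.
- **The 1 to 18% shrinkage is not a forecast.** It belongs to a stand-alone report with assumed odds ratios, not to the planned composite.
- **The unadjusted analyses are unaffected.** They come first in section 3.2, so a shift on adjustment would be visible, although not which covariate produced it.

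**Conclusion.** The point holds in a limited form. As written, the R5 regression adjusts for a measure that includes exposure after the fire, part of it counted from injury reports that airway damage could influence. Pooling that with pre-fire exposure can bias the Grenfell coefficient.

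Size and direction cannot be fixed from the documents. If damage does not drive later recorded exposure, the pooled adjustment is harmless in the illustration. If it does, the departure ranges from nil to −20% with balanced pre-fire exposure, and is +14% or −27% with a 0.3 SD imbalance at a = ∓0.4. All of this rests on the assumed 0.008 per SD and the assumed values of a and r.

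A reader might conclude that the pre-fire-only model is the correct one. That goes too far: a station path of 0.3 SD would bias it by about +9%. Neither model is clearly right alone, which is why both should be shown.

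**What to change.** Derive two variables from the LFB records, split at the date of the fire: non-Grenfell exposure before it, and exposure after it. Pre-specify the R5 regression and the secondary regressions with the pre-fire variable. Report alongside each the same model with post-fire exposure added, measured by the station-level operational-experience component. Keep post-fire individual injury reports out of the adjustment set. Present both estimates and describe neither as free of bias.

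The cost is a few sentences in sections 3.1 and 3.2 and one further model per outcome, provided the records carry dates, as their stated coverage of both periods implies. The main downside is that the pre-fire-only model can carry residual confounding through station or role; the second model shows how far the estimate moves. A lesser one is that the station-level component is still linked to employment records, so it can reflect changes of duty, though it is less open to differences in reporting.
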